## Specific Aim II: To evaluate in a variety of clinical care settings the effectiveness of a standardized PPE compliance auditing tool coupled with a tiered accountability framework.

**SIGNIFICANCE:** The lessons learned from hand hygiene improvement programs may be helpful when examining methods to audit and improve PPE compliance among HCP. Various innovative interventions to facilitate hand hygiene compliance have been developed over the past decade. These include visible and tactile monitors that alert the HCP to perform hand hygiene in real-time, user-friendly alcohol-based hand rub dispensers that provide easy access to hand hygiene materials, and enhanced monitoring tools. These interventions not only incorporate the practice of hand hygiene into the workflow of HCP but also explicitly emphasize the importance of performing this essential infection prevention practice. Nonetheless, even with advancements in hand hygiene is ultimately rooted in the behavior of the HCP, failure to develop interventions to drive expected behaviors will reduce the impact of these tools. PPE compliance is very similar, as even with advances in the PPE that may facilitate donning, use, and doffing, the underlying determinant of safe PPE utilization is rooted in HCP behavior.

Hand hygiene compliance monitoring has now become a central part of infection prevention programs at most healthcare facilities, and these data are being used on a large-scale as measures of healthcare quality. In Australia, for example, the creation of the National Hand Hygiene Initiative in 2009 required the reporting of hand hygiene compliance in all Australian hospitals using a standardized methodology. The development of a standardized measurement and education process for hand hygiene, the "Five Moments for Hand Hygiene" developed by the WHO, was a major advancement that provided healthcare facilities with a set of tools to improve hand hygiene compliance. In contrast, standardized tools for auditing PPE compliance akin to the "Five Moments" methodology are absent. Ideally, these tools should be guided by data on practices that increase the risk for PPE breaches and the associated contamination of HCP and the environment.

As noted previously, we have extensive experience in the creation and successful implementation of a hand hygiene compliance improvement program that partners standardized, wide-scale auditing of HCP practice with a foundational structure of data feedback, real-time peer-to-peer interventions to professionally redirect noncompliant behaviors, and performance accountability. Implemented in July 2009, the comprehensive program included extensive project planning, leadership buy-in and goal setting, financial incentives linked to performance, and use of a system-wide, shared accountability model. Compliance is monitored by direct observation of practice, and every inpatient and outpatient patient care area must designate a HCP to serve as an observer. Observers, once trained in the audit methodology, monitor locations other than their own on a monthly basis. This system has created an interdependence of unit leaders upon one another to provide important data to help drive improvement.

A central part of the program includes a formalized process for redirecting noncompliant behavior in real-time and a formal tiered accountability process that elevates units with compliance below institutional goals to receive more directed intervention. Using a tiered pyramid approach, unit leaders with compliance rates below institutional goals are made aware of their performance compared to their peers, and if improvement is not noted, enhanced interventions occur. This program covers over 200 distinct clinical units (inpatient, outpatient, and procedural) and has captured over 250,000 observations of practice to date. It has resulted in significantly improved and sustained compliance rates (from 52% at program start to 96% for the current fiscal year), has been associated with reductions in HAIs, and, most importantly, has help drive a culture where monitoring and real-time correction of HCP behaviors is expected and accepted as an important safety intervention. The success of this program was recognized in 2014 when the study manuscript was designated by SHEA as the year's top research paper published in the premier healthcare epidemiology journal, *Infection Control and Hospital Epidemiology*.

We propose that ensuring compliance with transmission-based precautions and PPE must be driven by the same tenets and interventions used in improving hand hygiene compliance. While novel, more "user-friendly" types of PPE may be necessary to facilitate compliance, failure to hardwire practice through standardized process monitoring, shared accountability for performance, and professional real-time reminders will limit the effectiveness of improved equipment. This study Aim will examine the utilization and impact of a standard PPE compliance auditing tool folded into a shared accountability program model. Our hypothesis is that such a tool will aid in capturing PPE compliance in a diversity of healthcare settings and that the overriding process will result in a sustained improvement in practice.

**INNOVATION:** The primary innovations of this Aim are the development and evaluation of a standardized tool to audit PPE compliance and the creation of a structured program to hardwire expected behaviors surrounding safe PPE use. We anticipate that this tool and program

structure can be utilized to improve practice in a wide-array of healthcare facility types, similar to the impact the standardized hand hygiene compliance tools and programs.

#### APPROACH:

#### **RESEARCH DESIGN AND METHODS:**

**Study Design:** 1) Audit tool development and field testing; 2) Prospective quasiexperimental phased implementation study.

**Tool Development and Initial Evaluation:** For this Aim, we will first develop a PPE compliance audit tool based on learnings from the simulation experiments in Aim I. Information on the types of breaches in PPE use and the practices that led to these breaches will inform the tool. A review panel of experts in infection prevention, PPE use, and occupational infection prevention (consisting of some members of the Advisory and Steering Committee) will independently review the tool for content validity. An initial evaluation of the tool will then occur as members of the Vanderbilt Epicenter team will perform direct observation of practices using the tool. These observations will occur in a variety of healthcare facility types (including adult inpatient units at a tertiary academic medical center and at a community-based hospital, pediatric inpatient units, outpatient hemodialysis units, and an inpatient rehabilitation hospital). Feedback from these pilot observations, including time to complete and ease of use, will lead to revision of the tool for the second part of this Aim.

#### Implementation Study:

**Study Population:** The initial implementation will occur on acute care inpatient units at Vanderbilt University Hospital (VUH), the Monroe Carell Jr. Children's Hospital at Vanderbilt (MCJCHV), and Williamson Medical Center (WMC). The target number of units will be 6 VUH, 6 MCJCHV, and 2 WMC units. All HCP on study units will be included for observation of practice.

#### Study Procedures:

**Study Outcomes:** Overall compliance with PPE use for patients placed in transmission-based precautions.

**Data Collection:** Trained observers will utilize the revised audit tool to capture compliance. A target of 500 observations of individual HCP PPE use events will be collected per month per study unit. This will provide ~42,000 observations for each study period (500 observations/month/unit \* 6 months \* 14 units). These observers will be formal Vanderbilt Epicenter personnel as well as unit and clinic HCP, modeled after the Vanderbilt Hand Hygiene Program described above. Observers will be trained on the use of the tool in a standardized fashion.

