#### SIGNIFICANCE:

#### Preventing Transmission of Contagious Pathogens in Healthcare Settings:

Healthcare-associated transmission of infectious pathogens can occur from numerous routes, including direct contact with infected patients, exposure to respiratory droplets in enclosed air spaces, and handling of contaminated objects within the patient environment. The resultant healthcare-associated infections (HAIs) have a dramatic impact on the health and safety of patients. Awareness of the incidence of a number of these events has led to marked improvement in targeted outcomes through comparative measurement, visible reporting of performance, and accountability through financial incentives. In contrast, awareness of the impact of these pathogens on the health and safety of the healthcare personnel (HCP) who care for patients infected with such pathogens is less well known. By nature of their occupation, HCP are at an increased risk of exposure to and subsequent infection by a variety of pathogens. HCP also serve as vectors for pathogen transmission through their frequent contact with patients colonized or infected with these organisms. Therefore, the prevention of transmission of these agents to HCP (a.k.a. "occupational infection prevention") is an important safety measure for both the individual HCP and his or her patients.

A foundational practice to prevent the spread of pathogens to HCP in healthcare settings is the use of transmission-based precautions. The basic concept of transmission-based precautions is using specific environmental controls and personal protective equipment (PPE) for pathogens based on their predominant mode of transmission. Used to augment Standard Precautions (i.e. core practices based on the principle that "all blood, body fluids, secretions, excretions except sweat, nonintact skin, and mucous membranes may contain transmissible infectious agents") that are applied to the care of all patients, transmission-based precautions include Contact, Droplet, and Airborne Precautions. Additional precautions include a combination of these three main types of precautions which are used for pathogens spread by multiple routes or that are highly contagious (Table 1).

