	Gloves	Gown	Surgical Mask	N95 Respirator or PAPR	Eye Protection	Full Body Covering (e.g. Hood, Apron, Leg Covering)	Negative Pressure Room	Examples of Pathogens for which Precaution Type is Used	
Contact	~	~						MDROs, C. difficile	
Droplet			✓	√ *			√ *	Seasonal influenza, B. pertussis	
Airborne				*			1	M. tuberculosis, measles	
Novel Respiratory Pathogen	*	*		~	*		V	Pandemic influenza, SARS-CoV, MERS-CoV	
EVD Precautions	*	~	√ (	or √*	*	~	√*	Ebola, Other VHF Agents	

Table 1: Summary	y of Transmission-Based Precaution Types and Components 

PAPR = Powered Air Purifying Respirator; SARS-CoV = Severe Acute Respiratory Syndrome Coronavirus; MERS-CoV = Middle East Respiratory Syndrome Coronavirus; EVD = Ebola Virus Disease; VHF = Viral Hemorrhagic Fever \* Use for aerosol-generating procedures (e.g. intubation, open suctioning of respiratory secretions, bronchoscopy)

The cases of HCP-acquired EVD have illuminated many important safety issues surrounding the use of transmission-based precautions and their associated PPE in healthcare facilities across the United States. When examining these issues, several key points are important to highlight:

- Transmission-based precaution utilization is common in acute care facilities.
- HCP compliance with the PPE used for transmission-based precautions is suboptimal.
- Exposure to patients with contagious pathogen infection or colonization even in the setting of PPE use can lead to pathogen contamination of HCP hands and the environment.
- HCP can become infected with pathogens targeted by transmission-based precautions and can serve as vectors of patient transmission in healthcare facilities.
- Factors that affect the appropriate use of PPE are numerous, complex, and not fully understood.
- Formal competency training on the use of and routine auditing of compliance with PPE and transmission-based precaution practices is lacking at most healthcare

facilities.

• Improving the effectiveness of PPE (through improved compliance) will require changing and hardwiring HCP behavior.

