## Study procedures:

Three transmissionbased precaution scenarios will be utilized (Table 2). These will involve Contact Precautions (PPE: gown and gloves), Droplet Precautions (PPE: surgical mask), and EVD-Precautions (PPE: PAPR, eve protection, hood, aown. double aloves. lea

coverings, and apron). For the Contact Precautions scenario, subjects will perform a brief history and abbreviated physical exam along with a simulated wound dressing change. For the Droplet Precautions scenario, subjects will perform a brief history and abbreviated physical examination along with management of a urinary catheter (including emptying of collection bag). For the EVD-Precautions scenario, subjects will perform a brief history and abbreviated physical exam along with medication administration through an intravenous catheter. Non-CDRT personnel will participate in both the Contact and Droplet scenarios (A-D in Table 2), while only CDRT members will participate in the EVD-Precautions scenario (E & F in Table 2). Each

scenario will have a standard 10 minute duration and a prolonged 20 minute duration (in which the exam is a standard physical exam) to assess the impact of prolonged PPE use on compliance.

Using a fluorescent compound to reproduce contaminants in assessing

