1) Awareness: If a unit performs below target compliance goals for two or more periods, the unit leadership will receive written/electronic communication regarding the unit's below target performance (see Sample Compliance Awareness Report, Appendix) and will be provided information about resources available to improve performance, including local peers/units who are engaged in best practices. To allow units ample opportunity to demonstrate improvement, they may receive up to two awareness intervention visits before escalation to the next level.

2) *Guided Engagement:* If performance does not improve after two awareness interventions, units will receive a guided intervention, which includes in-person sharing of performance and meaningful comparisons delivered by trained study personnel.

**Analysis:** The aggregate rates of PPE compliance will be compared between both study periods, with a null hypothesis that compliance will not significantly improve from the Baseline Monitoring Period to the Awareness and Accountability Period. The primary analysis will examine the aggregate compliance in all study units, with an additional analysis stratified by acute care facility. In addition, a more robust interrupted time-series regression analysis with Newey-West standard errors will be performed using bimonthly compliance rates.

**Limitations:** Even with a robust observation program, the number of instances of HCP PPE use observed will be only a small proportion of the total number of these opportunities. Compliance measurements from the observed events may not be representative of the total, as there may be a Hawthorne Effect on HCP compliance based on the presence of an observer. We have encountered this issue with the hand hygiene program as well. Because these interventions and programs are designed to alter HCP behavior, we have found that even with the Hawthorne Effect of direct observation, the provision of regular observation and real-time feedback when lapses are noted has led to a hardwiring to expected behavior (based on other measures of hand hygiene compliance such as patient and embedded observer reports). We

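### Aim II compares one crude compliance rate pooled over precaution types; if compliance differs by type, a shift in the type mix between periods moves the result without any change in behaviour

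*Protocol*

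**What the plan says.** All of this is in the protocol under Specific Aim II unless noted.

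- **Outcome** (Study Outcomes): "Overall compliance with PPE use for patients placed in transmission-based precautions". The opening Significance section says that "transmission-based precautions include Contact, Droplet, and Airborne Precautions", and it adds combined types.
- **Equipment by type.** Table 1 and the Aim I study procedures give different requirements: "Contact Precautions (PPE: gown and gloves), Droplet Precautions (PPE: surgical mask".
- **Sampling** (Data Collection): "A target of 500 observations of individual HCP PPE use events will be collected per month per study unit". The quota is set by unit and month. No quota or weight by precaution type is given.
- **Units** (Study Population): "The target number of units will be 6 VUH, 6 MCJCHV, and 2 WMC units".
- **Analysis.** Aggregate rates are compared between the Baseline Monitoring Period and the Awareness and Accountability Period, which follow one another and last 6 months each. "The primary analysis will examine the aggregate compliance in all study units, with an additional analysis stratified by acute care facility". An interrupted time series on bimonthly compliance rates, with Newey-West errors, is added.
- **Limitations.** Representativeness, the Hawthorne effect and institutional culture are discussed. The mix of precaution types is not.

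**The concern.** A pooled rate is a weighted average of type-specific rates, and the weights here are whatever mix of precautions happens to be in use when the auditors visit. The design is before-after with no concurrent control, so the difference between the two aggregates carries the conclusion about the accountability model. Any part of that difference caused by a changed mix would be credited to the model, or would offset its real effect.

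Two conditions must both hold for this to happen.

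1. **Compliance differs by type.** This is plausible. A Contact event can fail on either of two items and a mask-only event on one. Compliance also varies by item in the study cited in the Significance section: 25.7% noncompliance with gowns and 19.9% with gloves, a gap of 5.8 points. Aim I itself plans to compare lapse rates across precaution types.
2. **The mix differs between periods.** This is also plausible. Two consecutive 6-month periods cover different parts of the year, and Table 1 lists "Seasonal influenza" among the Droplet examples.

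The planned analyses do not remove the problem. The mix can change within each facility, so facility strata do not hold it fixed. The time series uses the same pooled rates, and Newey-West errors deal with autocorrelation, not with a change in composition that coincides with the change of phase.

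**Working it through.** **The plan's own figure.** Units: 6 + 6 + 2 = 14. Observations per period: 500 × 6 months × 14 units = 42,000, as stated ("42,000 observations for each study period (500 observations/month/unit"). The quota keeps the unit mix roughly constant, but it says nothing about type mix within a unit.

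**Inputs for the illustration**

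- Contact compliance p_C = 100% − 25.7% = 74.3%, from the gown figure in the Significance section. This is one component used as a stand-in for the whole event.
- Mask-only compliance p_M: not in the document. Assumed, range 60% to 90%.
- Mask-only share s of audited events: not in the document. Assumed to rise from 10% to 20%, or from 10% to 30%.
- Behaviour within type: unchanged between periods.
- Simplification: two types only. Airborne and combined precautions are left out.

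**Formulas**

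Aggregate = (1 − s) × p_C + s × p_M

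Drift = (s₂ − s₁) × (p_M − p_C)

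**One case in full** (p_M = 85%, share 10% to 20%)

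- Period 1: 0.90 × 0.743 + 0.10 × 0.85 = 0.7537
- Period 2: 0.80 × 0.743 + 0.20 × 0.85 = 0.7644
- Drift: 0.10 × (0.85 − 0.743) = +1.07 points

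**Range**

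| Assumed p_M | Drift, share 10% to 20% | Drift, share 10% to 30% |
|---|---|---|
| 60% | −1.43 points | −2.86 points |
| 70% | −0.43 | −0.86 |
| 74.3% (equal to Contact) | 0 | 0 |
| 80% | +0.57 | +1.14 |
| 85% | +1.07 | +2.14 |
| 90% | +1.57 | +3.14 |

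If the share falls instead of rising, every sign reverses.

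**With the mix held fixed.** Let w_k be one set of weights used in both periods. The standardised difference is Σ w_k × (p_k,period 2 − p_k,period 1). With unchanged behaviour each bracket is zero, so the drift is zero whatever the mix does.

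**The case against.** The strongest reply is that the effect is conditional and its size unsourced. The protocol gives no mask compliance rate and no precaution mix, so both the gap and the shift are assumed. If compliance is equal across types the drift is exactly zero. This stands, and it is why the point is worded conditionally and shown as a range.

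A second reply is that overall compliance is a defensible pragmatic target for a programme that covers every precaution type, that an observer must know the type to score an event, and that an analysis plan could add type-specific summaries. This stands in part. The type may well be recorded on the form. But the protocol itself fixes the outcome, the primary comparison and the only stratification, and none of them uses type. A supplementary table would leave the primary result exposed.

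Three stronger readings are tempting and are not supported.

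- A reader might infer that, with about 42,000 observations per period, such a drift would almost certainly be declared significant. That would treat observations clustered in 14 units as independent. The protocol names no such test for the aggregate comparison and gives no measure of clustering, so no z value can be attached to the drift.
- A reader might infer that a shift is assured because 6 of the 14 units are in a children's hospital. The unit targets do not change between periods, and the document gives no Droplet volume for paediatric units.
- A reader might infer that the drift favours the intervention. The calendar months of the periods are not legible in the public timeline, and two consecutive half-years could split a respiratory season between them. The direction is unknown.

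**Conclusion.** The point holds in conditional form. The primary comparison is a crude aggregate over precaution types with different requirements, and no planned element fixes the mix or adjusts for it. If compliance differs by type and the mix changes between periods, the estimate is biased by the product of the two differences. More observations do not reduce that bias.

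Under the stated assumptions (Contact at 74.3%, mask-only share from 10% to 20%), the drift is about +0.6 to +1.6 points for mask compliance of 80% to 90%, −1.4 points at 60%, and zero at equality. This does not show that the Aim II result will be wrong or in which direction it would err. It shows that an uncontrolled before-after comparison leaves open an avoidable alternative explanation, one that can be closed cheaply before the audit tool is built.

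**What to change.** - Add precaution type as a required field on the audit tool, which is still to be developed.
- Make the primary period comparison one that is standardised to a single prespecified type mix, for example the pooled mix over both periods. State in advance how sparse types are collapsed, and weight at facility rather than unit level where unit-by-type cells are empty. Adjusting for type in the model would serve equally well.
- Report type-specific rates for each period, and keep the crude aggregate as a descriptive figure.
- Use the standardised rate or a type term in the interrupted time series too, so that both analyses address the same question.

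Fixed audit quotas by type are not a good substitute. They impose different weights, change what the rate represents, and may be unattainable in months when few patients are in a given type of precaution.

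The cost is one field on the form, a weighted summary or one model term, and slightly lower precision where a type is rare. The change removes drift from the type mix only. It does not deal with other changes over time in a design without a concurrent control.
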